Should a given patient experience any of the above DLTs at any time after the completion of the second cycle of co-administration of galinepimut-S in combination with pembrolizumab, the frequency of administration of galinepimut-S will be reduced by 50% for the next cycle, but pembrolizumab will continue as scheduled. If another DLT occurs in that next cycle, the frequency of administration of galinepimut-S will be reduced by 50% for the subsequent 2 cycles, but pembrolizumab will continue as scheduled. If a DLT occurs after these dose modifications in subsequent cycles, the patient will be discontinued from the study.

The above dose density modifications in response to DLTs is further summarized in the bulleted list of actions below:

- First DLT → skip the next GPS inoculation (scheduled for the next cycle, i.e., 3 wks ahead) and administer GPS 6 wks ahead (i.e., ‘spread out’) **once thereafter**, i.e. **for 1 additional cycle** → DLT resolution → Return to per protocol schedule of GPS administration
- Second DLT (after reverting to the per protocol schedule) → skip the next GPS inoculation (scheduled for the next cycle, i.e., 3 wks ahead) and administer GPS 6 wks ahead (i.e., ‘spread out’) **twice thereafter**, i.e. **for**

2 additional cycles → DLT resolution → Return to per protocol schedule of GPS administration

- Third DLT (occurring either after reverting to the per protocol schedule or during the ‘spread out’ schedule to manage the 2nd DLT above) → Discontinue patient from study.

N.B.: In all above modifications of the dose density of galipepimut-S, as all intervals (in weeks) between 2 successive GPS administrations are multiples of three (3) by design, following these rules, co-administration with pembrolizumab is always secured.

Stopping rules:

- Development of any SAEs at least “possibly attributable” to the study agent(s) in 2 out of the first 6 patients in the study. In this case, the upper 90% one-sided CI bound for 2 patients with SAEs within 6 patients would be 66.7%, consistent with an excessive rate of toxicity.
- The fraction of patients experiencing an SAE at least “possibly attributable” to the study agent(s) exceeds 1/3, at any time during study implementation beyond the first 6 patients.
- Death at least “possibly attributable” to the study investigational agent(s) within 30 days after the administration of the investigational treatment (GPS plus pembrolizumab)
- Development of grade 3 or higher colitis/diarrhea,

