5.3.6.1. Dose-Limiting Toxicities

All toxicities will be graded using National Cancer Institute Common Terminology Criteria for Adverse Events (NCI CTCAE) Version 5.0, (published in November 2017), as per the following link:

https://ctep.cancer.gov/protocolDevelopment/electronic_applications/docs/CTCAE_v5_Quick_Reference_5x7.pdf.

For patients enrolled across all active solid tumor cohorts (colorectal, ovarian, small cell lung cancer, breast cancer), the dose-limiting toxicity (DLT) window of observation will be at least one (1) cycle following the co-administration of galinpepimut-S in combination with pembrolizumab. A DLT is judged by the investigator to be possibly, probably, or definitely related to study drug administration. AML-specific DLTs will be considered separately ([Section 5.3.6.2](#)).

The occurrence of any of the following toxicities will be considered a DLT (except for AML; please see [Section 5.3.6.2](#)), if judged by the investigator to be possibly, probably, or definitely related to study drug administration:

1. Grade 4 nonhematologic toxicity (not laboratory)
2. Grade 4 hematologic toxicity lasting ≥ 7 days, except thrombocytopenia:
 - Grade 4 thrombocytopenia of any duration
 - Grade 3 thrombocytopenia associated with bleeding
3. Any nonhematologic AE \geq Grade 3 in severity should be considered a DLT, with the following exceptions: Grade 3 fatigue lasting ≤ 3 days; Grade 3 diarrhea, nausea, or vomiting without use of anti-emetics or anti-diarrheals per standard of care; Grade 3 rash without use of corticosteroids or anti-inflammatory agents per standard of care.
4. Grade 3 nonhematologic toxicity (not laboratory) lasting > 3 days despite optimal supportive care.
5. Any Grade 3 or Grade 4 nonhematologic laboratory value if:

- Clinically significant medical intervention is required to treat the patient, or
 - The abnormality leads to hospitalization, or
 - The abnormality persists for > 1 week.
 - The abnormality results in a drug-induced liver injury (DILI)
 - Exceptions: clinically nonsignificant, treatable, or reversible laboratory abnormalities, including liver tests, uric acid, etc.
6. Febrile neutropenia (FN) Grade 3 or Grade 4:
 - Grade 3 is defined as absolute neutrophil count (ANC) < 1000/mm³ with a single temperature of > 38.3°C (101°F) or a sustained temperature of ≥ 38°C (100.4°F) for more than 1 hour

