- In the next 6 patients (patients 7 to 12), if again, 2 or fewer of these patients have DLTs observed, enrollment can continue. If DLTs are observed in more than 2 of patients 7 to 12, the time interval between galinpepimut-S doses for the inoculation following the one associated with the DLT will be doubled, , but pembrolizumab will continue as scheduled.
- If DLTs are observed in more than 2 patients of the first 6 (patients 1 to 6) and again in more than 2 patients of the next 6 (patients 7 to 12), the time interval between galinpepimut-S doses will be doubled for two (2) inoculations following the one associated with the DLT. For example, if galinpepimut-S was given on a Q3W schedule before the DLT occurred, it should be given Q6W for the 2 immediately subsequent administrations after the dosing event associated with the DLT, while keeping the pembrolizumab dose and frequency stable.

- If DLTs continue to be observed above 2 per every 6 patients beyond these first 12 patients, and even after the changes in administration of galinpepimut-S, the study will be stopped and the safety data will be examined by the sponsor in consultation with investigators in order to determine how to proceed or whether to discontinue the study.
- Should a given patient experience any of the above DLTs at any time after the completion of the first cycle of co-administration of galinpepimut-S in combination with pembrolizumab, the time interval between galinpepimut-S doses for the inoculation following the one associated with the DLT will be doubled, but pembrolizumab will continue as scheduled.
- If another DLT occurs in that next cycle, the time interval between galinpepimut-S doses will be doubled for two (2) inoculations following the one associated with the DLT, but pembrolizumab will continue as scheduled.
- If no DLTs re-occur after the above periods of doubly 'spaced out' administrations, then the patient should revert back to the initial GPS Q3W schedule (as per the initial dosing frequency/ investigational agent administration schedule).
- If a DLT occurs after these dose modifications in subsequent cycles, the patient will be discontinued from the study.

The above dose density modifications in response to DLTs is further summarized in the bulleted list of actions below:

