- First DLT → skip the next GPS inoculation (scheduled for the next cycle, i.e., 3 wks ahead) and administer GPS 6 wks ahead (i.e., 'spread out') **once thereafter**, i.e. **for 1 additional cycle** → DLT resolution → Return to per protocol schedule of GPS administration
- Second DLT (after reverting to the per protocol schedule) → skip the next GPS inoculation (scheduled for the next cycle, i.e., 3 wks ahead) and administer GPS 6 wks ahead (i.e., 'spread out') **twice thereafter**, i.e. **for 2 additional cycles** → DLT resolution → Return to per protocol schedule of GPS administration

- Third DLT (occurring either after reverting to the per protocol schedule or during the ‘spread out’ schedule to manage the 2nd DLT above) → Discontinue patient from study.
- N.B.: In all above modifications of the dose density of galipepimut-S, as all intervals (in weeks) between 2 successive GPS administrations are multiples of three (3) by design, following these rules, co-administration with pembrolizumab is always secured.

Stopping Rules:

- Development of any SAEs at least “possibly attributable” to the study agent(s) in 2 out of the first 6 patients in the study. In this case, the upper 90% one-sided CI bound for 2 patients with SAEs within 6 patients would be 66.7%, consistent with an excessive rate of toxicity.
- The fraction of patients experiencing an SAE at least “possibly attributable” to the study agent(s) exceeds 1/3, at any time during study implementation beyond the first 6 patients.
- Death at least “possibly attributable” to the study agent(s) within 30 days after the administration of the investigational treatment (GPS plus pembrolizumab).

If the study is stopped due to activation of the above rules, the safety data will be examined by the Sponsor in consultation with investigators in order to determine how to proceed or whether to discontinue the study at large.

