- If no DLTs re-occur after the above periods of doubly 'spaced out' administrations, then the patient should revert back to the initial GPS Q3W schedule (as per the initial dosing frequency/ investigational agent administration schedule).
- If a DLT occurs after these dose modifications in subsequent cycles, the patient will be discontinued from the study.

The above dose density modifications in response to DLTs is further summarized in the bulleted list of actions below:

- First DLT → skip the next GPS inoculation (scheduled for the next cycle, i.e., 3 wks ahead) and administer GPS 6 wks ahead (i.e., 'spread out') **once thereafter**, i.e. **for 1 additional cycle** → DLT resolution → Return to per protocol schedule of GPS administration
- Second DLT (after reverting to the per protocol schedule) → skip the next GPS inoculation (scheduled for the next cycle, i.e., 3 wks ahead) and administer GPS 6 wks ahead (i.e., 'spread out') **twice thereafter**, i.e. **for 2 additional cycles** → DLT resolution → Return to per protocol schedule of GPS administration

- Third DLT (occurring either after reverting to the per protocol schedule or during the ‘spread out’ schedule to manage the 2nd DLT above) → Discontinue patient from study.
- N.B.: In all above modifications of the dose density of galipepimut-S, as all intervals (in weeks) between 2 successive GPS administrations are multiples of three (3) by design, following these rules, co-administration with pembrolizumab is always secured.

Stopping rules (for AML patients):

- Development of any SAEs at least “possibly attributable” to the study agent(s) in 2 out of the first 6 patients in the study. In this case, the upper 90% one-sided CI bound for 2 patients with SAEs within 6 patients would be 66.7%, consistent with an excessive rate of toxicity.
- The fraction of patients experiencing an SAE at least “possibly attributable” to the study agent(s) exceeds 1/3, at any time during study implementation beyond the first 6 patients.
- Death at least “possibly attributable” to the study agent(s) within 30 days after the administration of the investigational treatment (GPS plus pembrolizumab)

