5.3.7. Toxicity Management of Injection-reactions Related to Galinpepimut-S

Expected AEs from study treatment injection (any component of galinpepimut-S, excluding GM-CSF) include local erythema, edema, itching, and persistent induration at the site of injection. These events are usually mild and may appear after each administration of the study treatment. These Grade 1 and Grade 2 local injection site reactions may resolve spontaneously but they can be treated with topical creams (e.g., aloe), analgesics and/or antihistamines as per investigative site guidelines and will not require treatment interruptions or discontinuation.

Local injection site reactions of grade 3 or higher may require antihistamines, non-steroidal anti-inflammatory agents, and/or steroid therapy as per investigative site guidelines. Re-challenge of a patient after a local grade 3 event will need to be discussed with the medical monitor. Premedication with diphenhydramine 50 mg (or equivalent) and/or paracetamol (325 to 1,000 mg) at least 30 minutes prior to the next treatment injection will be required for the re-challenge. If local toxicity of grade 3 or higher persists, the patient will be moved to the off- treatment follow-up period.

Systemic events of grade 3 or grade 4 toxicity that are considered possibly related to study treatment (any component of galinpepimut-S, excluding GM-CSF) should be quickly discussed with the medical monitor. Autoimmune or hypersensitivity reactions to components of the study treatment or skin test antigens are possibilities. Patients who develop events of non-skin related autoimmune disorders or anaphylactic reactions considered possibly related to the study treatment or any of its components (other than

GM-CSF) may require appropriate care with epinephrine, antihistamines, vasopressors, fluids, and/or steroid therapy as per investigative site guidelines. The medical monitor should be contacted, and these patients will be moved to the off- treatment follow-up period.

Toxicity events related to GM-CSF should be discussed expeditiously with the medical monitor and consideration will be made to either allow the patient to continue the study treatment with or without GM-CSF or to move that particular patient to the off- treatment follow-up period. Treatment of GM-CSF related events are to be treated as per investigative site guidelines.

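### After a related Grade 3-4 anaphylactic or non-skin autoimmune DLT in the solid tumor arms, the DLT ladder re-doses galinpepimut-S while Section 5.3.7 takes the patient off treatment, and no text says which prevails

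*Combined protocol and SAP*

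**What the plan says.** **DLT definition, solid tumors (Section 5.3.6.1).** Items 1 and 3 make a Grade 4 nonhematologic toxicity a DLT, and likewise any nonhematologic event of Grade 3 or above, if at least possibly related to study drug. Item 3 reads "in severity should be considered a DLT, with the following exceptions". The exceptions concern fatigue, gastrointestinal symptoms and rash.

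**Per-patient ladder (Section 5.3.6.1; repeated in the synopsis).** The prose opens with "Should a given patient experience any of the above DLTs at any time after the completion of the first cycle of co-administration". The bulleted summary gives the action at a first DLT: "skip the next GPS inoculation (scheduled for the next cycle, i.e., 3 wks ahead) and administer GPS 6 wks ahead". A second DLT leads to two spaced-out doses. Discontinuation comes at the third.

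**AML arm.** Section 5.3.6.2 repeats the ladder, including the bullet that begins "Third DLT (occurring either after reverting to the per protocol schedule or during the". The AML part of the synopsis starts it one cycle later: "Should a given patient experience any of the above DLTs at any time after the completion of the second cycle of co-administration".

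**Reaction management (Section 5.3.7).** For anaphylactic reactions and non-skin autoimmune disorders possibly related to the vaccine or its components other than GM-CSF: "The medical monitor should be contacted, and these patients will be moved to the off- treatment follow-up period". For local reactions a second attempt is possible: "Re-challenge of a patient after a local grade 3 event will need to be discussed with the medical monitor", with premedication required. After that, "If local toxicity of grade 3 or higher persists, the patient will be moved to the off- treatment follow-up period".

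**The concern.** One event receives two opposite instructions. A site working from the DLT section, or from the synopsis alone, would schedule another injection of the suspected agent after a severe anaphylactic or autoimmune reaction. A site working from Section 5.3.7 would stop.

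The synopsis makes the first route easier to follow. It prints the ladder, and for reactions after galinpepimut-S its Safety Assessments text refers the reader to Section 5.3.6, where the ladder sits, and not to Section 5.3.7.

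What is at stake is individual safety. Such events need not be common for the wrong instruction to do serious harm.

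**Working it through.** No power, alpha or event rate enters. The check compares the rules and counts doses.

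**1. Do the rules cover the same event?** Section 5.3.6.1 requires Grade 3 or higher, nonhematologic, and at least possibly related to study drug. Anaphylaxis and non-skin autoimmune events are not among the item 3 exceptions. The Section 5.3.7 sentence requires a possible relation to galinpepimut-S or its components other than GM-CSF and sets no grade limit. The overlap is therefore Grade 3-4 events at least possibly attributed to galinpepimut-S. Events attributed only to pembrolizumab or only to GM-CSF are outside it.

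**2. What does each rule instruct?**

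| | Ladder (5.3.6.1) | Section 5.3.7 |
|---|---|---|
| First event | skip one dose, re-dose at 6 weeks | off treatment |
| Second event | two more spaced doses | not reached |
| Third event | discontinue | not reached |

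**3. How many further doses?** Put the first event at week 0 on the every-3-week schedule and assume each re-dose reproduces it.
- Doubled interval: 2 × 3 = 6 weeks, as the ladder states.
- Dose at week 0 + 6 = 6: second DLT.
- Dose at week 6 + 6 = 12: third DLT, discontinue.
- Ladder: 2 further doses. Section 5.3.7: 0.

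**4. Which planned doses are exposed to the 6-week step?** The planned galinpepimut-S doses (Section 3.1.1 and Table 8) are at weeks 0, 3, 6, 9, 12, 15, 21, 24, 27, 30, 33, 36, 48, 60, 72 and 84, which makes 16. Co-administration starts at week 6, so its first cycle ends at week 6 + 3 = 9. The every-3-week doses at week 9 or later are weeks 9, 12, 15, 21, 24, 27, 30, 33 and 36, which makes 9 of 16.

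**5. Does anything rank the rules?**
- The only override attached to the DLT actions is for the stopping rules. These work at study level: related SAEs in 2 of the first 6 patients, a fraction above 1/3 afterwards, or a related death within 30 days. They do not refer to Section 5.3.7.
- Section 4.2.1 allows withdrawal in the patient's interest but does not require it.
- Table 6 requires permanent discontinuation for Grade 3-4 reactions, but it is written for pembrolizumab infusion reactions.
- Sections 5.3.6.1 and 5.3.7 do not refer to each other.

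**6. Does the same hold in AML?** Section 5.3.6.2 counts as DLTs only events in the first 8 weeks from the first galinpepimut-S dose, and says other toxicities are not dose-limiting. Its prose ladder starts after the first co-administration cycle, at week 9. Read strictly, 9 > 8, so no event in the ladder's period is a DLT. The synopsis also gives a window of at least 8 weeks from the first pembrolizumab dose, which runs to week 6 + 8 = 14 or later. Its own ladder starts after the second co-administration cycle, at week 12, so on that wording there is some overlap. The AML reach cannot be settled from the text.

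**The case against.** The strongest reply is that the ladder presupposes a patient still on treatment. Section 5.3.7 is specific and mandatory; once the patient is off treatment there is no next inoculation to space. The protocol's structure supports this. The ladder also keeps pembrolizumab on schedule after a DLT, yet Table 5 permanently stops pembrolizumab for Grade 3-4 pneumonitis and myocarditis, so the ladder can hardly be meant to override agent-specific rules. It also has implied exceptions: Grade 5 events, and DLTs defined by discontinuation, cannot be re-dosed.

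There are practical safeguards too. Section 4.2.2 has the investigator confer with the sponsor after a serious or intolerable event, Section 4.2.1 permits removal from treatment, Section 6.4.1.3 requires SAE reports within 24 hours, and Section 5.3.7 calls for medical-monitor contact.

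All of this stands as a reason to expect the right outcome at most sites. It does not remove the conflict, because each step is inference or discretion and none states precedence. Applied as written, the ladder still schedules the dose.

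For local Grade 3 reactions the two rules agree on a first re-dose, although the ladder omits the premedication and medical-monitor discussion. They part only if toxicity of Grade 3 or higher persists.

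**Conclusion.** The conflict is real in the solid tumor arms, for related Grade 3-4 anaphylactic or non-skin autoimmune events after the first co-administration cycle. Its size is 2 further doses against 0. This assumes the every-3-week schedule, recurrence at each re-dose, and a literal reading of the ladder. A literal re-dose is unlikely, so the case for change rests on the severity of a wrong dose and the small cost of preventing it.

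Stronger readings that a reader might infer are not supported:
- **That the 6-week re-dose applies to all 13 doses from week 9 onward.** Four of these (weeks 48, 60, 72 and 84) are every-12-week doses; 13 − 4 = 9.
- **That the ladder could allow a third re-dose when every dose reproduces the reaction.** A third requires a return to the 3-week schedule after an uneventful dose, which contradicts that premise.
- **That AML is affected to the same extent.** The 8-week DLT limit leaves this open.
- **That the safety data bound the frequency.** The Grade 1-2 injection-site findings in the summary of 122 patients (Section 1.3.1.1) concern local reactions, not the systemic events at issue.
- **That the Grade 3 panmyositis on galinpepimut-S plus nivolumab (Section 1.1.2.2.3) shows the risk.** It is context only; the protocol does not attribute it to galinpepimut-S specifically.

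**What to change.** Add to the DLT action lists in Sections 5.3.6.1 and 5.3.6.2 and to both synopsis lists:

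*Section 5.3.7 takes precedence over the spacing/re-dosing steps: a patient with an anaphylactic reaction or non-skin autoimmune event possibly related to galinpepimut-S, or persistent local Grade 3 or higher toxicity, moves to off-treatment follow-up and is not re-dosed. Any re-dose after a first local Grade 3 reaction requires the Section 5.3.7 medical-monitor discussion and premedication.*

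In the synopsis Safety Assessments, change the reference for drug-administration reactions from Section 5.3.6 to Sections 5.3.6 and 5.3.7.

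The cost is two sentences repeated in four lists and one cross-reference. DLT definitions and counts are unchanged, and no procedure is added beyond what Section 5.3.7 already requires.

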5.3.8. Definition of an Overdose of Investigational Agents for This Protocol

For this trial (a fixed-dose regimen), an overdose will be defined as $\geq 1,000$ mg (5 times the dose) of pembrolizumab. No specific information is available on the treatment of overdose of pembrolizumab. In the event of overdose, the patient should be observed closely for signs of toxicity. Appropriate supportive treatment should be provided if clinically indicated.

No overdose is defined for galipepimut-S.

5.3.9. Toxicity Management of Known/Expected AEs Associated with the Continuing Use of Hypomethylating Agents (HMAs) in Patients Enrolled in the AML Arm

Dose modifications for HMA-related (known/expected) toxicities -for either azacitidine or decitabine- in AML patients will be based on the respective US Prescribing Information for these products. These documents are included as Appendices 12.1 and 12.2.

5.3.9.1. Toxicity Profile and Dose Modifications for Azacitidine (AML Patients) (Vidaza® US Prescribing Information; Appendix 12.1)

Most common adverse reactions (>30%) of azacitidine administered by the subcutaneous route are: nausea, anemia, thrombocytopenia, vomiting, pyrexia, leukopenia, diarrhea, injection site erythema, constipation, neutropenia and ecchymosis. Most common adverse reactions by the IV route also included petechiae, rigors, weakness and hypokalemia.

Adverse reactions most frequently ($\geq 2\%$) resulting in medical/clinical intervention and/or dose modification in patients receiving azacitidine (S.C. or IV Route) are as follows:

- Discontinuation: leukopenia, thrombocytopenia, neutropenia.
- Dose Held: leukopenia, neutropenia, thrombocytopenia, pyrexia, pneumonia, febrile neutropenia.
- Dose Reduced: leukopenia, neutropenia, thrombocytopenia.

Dose Modifications:

A. For hematologic toxicity

For patients with baseline (start of treatment) $WBC \geq 3.0 \times 10^9/L$, $ANC \geq 1.5 \times 10^9/L$, and platelets $\geq 75.0 \times 10^9/L$, adjust the dose as follows, based on nadir counts for any given cycle:

Nadir Counts		% Dose in the Next Course
ANC ($\times 10^9/L$)	Platelets ($\times 10^9/L$)	
Less than 0.5	Less than 25	50%
0.5 –1.5	25-50	67%
Greater than 1.5	Greater than 50	100%

For patients whose baseline counts are $WBC < 3.0 \times 10^9/L$, $ANC < 1.5 \times 10^9/L$, or platelets $< 75.0 \times 10^9/L$, base dose adjustments on nadir counts and bone marrow biopsy cellularity at the time of the nadir as noted below, unless there is clear improvement in differentiation (percentage of mature granulocytes is higher and ANC is higher than at onset of that course) at the time of the next cycle, in which case continue the current dose.

WBC or Platelet Nadir % decrease in counts from baseline	Bone Marrow Biopsy Cellularity at Time of Nadir (%)		
	30-60	15-30	Less than 15
50 - 75 Greater than 75	% Dose in the Next Course		
	100	50	33
	75	50	33

If a nadir as defined in the table above has occurred, give the next course 28 days after the start of the preceding course, provided that both the WBC and the platelet counts are greater than 25% above the nadir and rising. If a greater than 25% increase above the nadir is not seen by day 28, reassess counts every 7 days. If a 25% increase is not seen by day 42, reduce the scheduled dose by 50%.

B. For non-hematologic (serum electrolytes and renal) toxicity

If unexplained reductions in serum bicarbonate levels to less than 20 mEq/L occur, reduce the dosage by 50% for the next course. Similarly, if unexplained elevations of BUN or serum creatinine occur, delay the next cycle until values return to normal or baseline and reduce the dose by 50% for the next course.

5.3.9.2. Toxicity Profile and Dose Modifications for Decitabine (AML Patients) (Dacogen® US Prescribing Information; Appendix 12.2)

Most common adverse reactions (> 50%) seen during decitabine therapy include neutropenia, thrombocytopenia, anemia, and pyrexia.

Adverse reactions most frequently ($\geq 1\%$) resulting in medical/clinical intervention and/or dose modification in patients receiving decitabine are as follows:

- Discontinuation: thrombocytopenia, neutropenia, pneumonia, Mycobacterium avium complex infection, cardio-respiratory arrest, increased blood bilirubin, intracranial hemorrhage, abnormal liver function tests.
- Dose Delayed: neutropenia, pulmonary edema, atrial fibrillation, central line infection, febrile neutropenia.
- Dose Reduced: neutropenia, thrombocytopenia, anemia, lethargy, edema, tachycardia, depression, pharyngitis.

Dose Modifications:

A. For hematologic toxicity

If hematologic recovery from a previous decitabine treatment cycle requires more than 6 weeks, delay the next cycle of decitabine therapy and reduce decitabine dose temporarily by following this algorithm:

- Recovery requiring more than 6, but less than 8 weeks: Delay DACOGEN dosing for up to 2 weeks and reduce the dose temporarily to 11 mg/m² every 8 hours (33 mg/m²/day, 99 mg/m²/cycle) upon restarting therapy.
- Recovery requiring more than 8, but less than 10 weeks: Perform bone marrow aspirate to assess for disease progression. In the absence of progression, delay the decitabine dose up to 2 more weeks and reduce the dose to 11 mg/m² every 8 hours (33 mg/m²/day, 99 mg/m² /cycle) upon restarting therapy, then maintain or increase dose in subsequent cycles as clinically indicated.

B. For non-hematologic toxicity

Delay subsequent decitabine treatment for any the following non-hematologic toxicities and do not restart until toxicities resolve:

- Serum creatinine ≥ 2 mg/dL
- SGPT, total bilirubin ≥ 2 x ULN
- Active or uncontrolled infection

